All information pertaining to AEs noted during the study will be listed by subject, detailing the verbatim description given by the Investigator, preferred term, system organ class, start date, stop date, severity, action taken regarding study drug, corrective treatment, outcome, and drug relatedness along with the treatment emergent flag and subjects who prematurely discontinued from study flag. The event onset will also be shown relative (in number of days) to date of first application.

10.3. Local Tolerability Assessment

Investigator Local Tolerability Assessments will be summarized at Baseline, Week 2, and Week 4. Irritation reactions are graded using the following dermal response scale below. The investigator assessments will be conducted by the investigator prior to study drug application in the clinic.

Dermal Response

- 0 = no evidence of irritation
- 1 = minimal erythema, barely perceptible
- 2 = definite erythema, readily visible; minimal edema or minimal papular response
- 3 = erythema and papules
- 4 = definite edema
- 5 = erythema, edema and papules
- 6 = vesicular eruption
- 7 = strong reaction spreading beyond application site

Other Effects

- A = slight glazed appearance
- B = marked glazing
- C = glazing with peeling and cracking
- D = glazing with fissures
- E = film of dried serous exudates
- F = small petechial erosions and/or scabs
- G = no other effects

The investigator assessments will be conducted by the investigator prior to study drug application in the clinic. Frequency counts and percentages of the numeric application site reaction scores will be summarized at each study visit. Any additional information collected on the investigator's tolerance assessment that are not included in the summaries will be presented in listings.

The Subject Local Tolerability Assessment will be summarized at Baseline and Week 2. This assessment will be administered by the site 10 to 15 minutes after study drug application in the clinic at Baseline and at Week 2. Response may be by the patient and/or parent/caregiver, as deemed appropriate by the Investigator.

Grade	Sensation following Drug Application
0 (none)	No sensation
1 (mild)	Slight warm, tingling sensation; not really bothersome
2 (moderate)	Definite warm, tingling sensation that is somewhat bothersome
3 (severe)	Hot, tingling/stinging sensation that has caused definite discomfort

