### 7.1.7 Local Tolerability Assessment

**Investigator** Local Tolerability Assessment will be performed as follows:

- Baseline, Week 2, and Week 4

Application site reactions will be graded at the timepoints outlined in the Schedule of Visits and Assessments ([Section 2](#)). Irritation reactions are graded using the scale detailed in the following section ([Berger 1982](#)). Reactions at the site of product application, which may occur post-Baseline, should be differentiated from the preexisting inflammation associated with the subject's plaque psoriasis.

The investigator assessments will be conducted by the investigator prior to study drug application in the clinic.

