### **8.3.2 Local Tolerance Assessment**

For the Investigator's assessment the numeric application site reaction scores will be summarized individually by using number and percentage of subjects by visit.

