### Appendix 3. Investigator Global Assessment

Scale	Grade	Description
0	Clear	

• Plaque thickening = no elevation or thickening over normal skin

• Scaling = no evidence of scaling

• Erythema = none (no residual red coloration but post-inflammatory hyperpigmentation may be present)

1	Almost Clear	

• Plaque thickening = none or possible thickening but difficult to ascertain there is a slight elevation above normal skin level

• Scaling = none or residual surface drying and scaling

• Erythema = light pink coloration

2	Mild	

• Plaque thickening = slight but definite elevation

• Scaling = fine scales partially or mostly covering the lesions

• Erythema = light red coloration

3	Moderate	

• Plaque thickening = moderate elevation with rounded or sloped edges

• Scaling = most lesions at least partially covered

• Erythema = definite red coloration

4	Severe	

• Plaque thickening = marked or very marked elevation typically with hard or sharp edges

• Scaling = non-tenacious or thick tenacious scale, covering most or all of lesions

• Erythema = very bright red coloration; extreme red coloration; deep red coloration

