8.2. Baseline Values

Unless otherwise noted, baseline is defined as the last non-missing value recorded prior to the first application of study drug. When applicable, unscheduled visits will be used in the determination of baseline values.

For subject local tolerability assessment, baseline is derived as the last non-missing measurement taken on Day 1 of first application of study drug. Baseline investigator local tolerability assessment is the last non-missing assessment prior to the first dose.

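### The investigator irritation score is summarized visit by visit but never within child, so the planned table bounds, but cannot identify, how many children worsened on treatment

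*SAP*

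**What the plan says.** SAP 10.3 names the visits, "Investigator Local Tolerability Assessments will be summarized at Baseline, Week 2, and Week 4", and the statistic, "Frequency counts and percentages of the numeric application site reaction scores will be summarized at each study visit". Protocol 8.3.2 agrees: "numeric application site reaction scores will be summarized individually by using number and percentage of subjects by visit". Neither section names a change from Baseline, a shift table, a count of children who worsened, or a worst post-baseline score.

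SAP 8.2 nevertheless defines a reference value: "Baseline investigator local tolerability assessment is the last non-missing assessment prior to the first dose". In the planned outputs this value is used only as the Baseline row of the by-visit table.

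Protocol 7.1.7 tells raters that application-site reactions "should be differentiated from the preexisting inflammation" of the child's psoriasis. Footnote e of the visit schedule, in both documents, repeats this. In each place the instruction concerns reactions arising after Baseline. It gives no method and does not say how plaques are to be scored at Baseline, before any cream has been applied.

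SAP section 5 also plans by-subject listings of individual data.

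**The concern.** Tolerability is a primary endpoint (Protocol 5.2.1), and the study has one open-label treatment and no vehicle arm, so each child's own pre-dose state is the only available reference. The plan uses that reference elsewhere. Vital signs get change from baseline and body weight a shift table (SAP 10.4), laboratory tests get both (SAP 10.7), and the TEAE definition includes conditions that worsened on treatment (SAP 10.2). The irritation score gets neither.

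The by-visit table also carries weight of its own. Under Protocol 7.7.1 a site reaction becomes an adverse event only if it leads to intervention or to suspending or stopping the drug. Milder irritation may therefore appear in no other planned summary of the investigator's findings. At Week 4 the investigator score is the only local tolerability assessment scheduled.

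The Baseline score need not be 0. Every child enters with IGA of at least 2, which Protocol Appendix 3 describes as raised plaques with "Erythema = light red coloration"; IGA 3 is redder. The irritation scale in SAP 10.3 has "2 = definite erythema, readily visible; minimal edema or minimal papular response" and "3 = erythema and papules". The overlap is loose at IGA 2 and closer at IGA 3. Without a Baseline scoring rule, one rater could grade a plaque 0 and another could give it a higher score. If plaques are scored at Baseline, a falling percentage could be taken to mean that nobody developed new irritation.

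**Working it through.** **Inputs.** N = 20 (Protocol 8.1.3, approximate). The documents give no expected distribution, target or precision for this score, so there is no figure of the plan's own to reproduce. The counts b (children at grade 2 or more at Baseline) and w (children at grade 2 or more at a later visit) are assumed below, and all scores are taken as available.

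**Step 1: what two by-visit counts determine.** Let x be the number of children newly at grade 2 or more. The other w − x were already there at Baseline, so w − x cannot exceed b. Also, x cannot exceed w, or the N − b children who started below grade 2. Hence

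max(0, w − b) ≤ x ≤ min(w, N − b).

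| b | w | By-visit table reads | Newly at grade 2 or more | % of 20 |
|---|---|---|---|---|
| 10 | 7 | 50%, then 35% | max(0, −3) = 0 to min(7, 10) = 7 | 0 to 35% |
| 12 | 6 | 60%, then 30% | 0 to min(6, 8) = 6 | 0 to 30% |
| 12 | 4 | 60%, then 20% | 0 to min(4, 8) = 4 | 0 to 20% |
| 4 | 4 | 20%, then 20% | 0 to min(4, 16) = 4 | 0 to 20% |
| 0 | 4 | 0%, then 20% | max(0, 4) = 4 to min(4, 20) = 4 | exactly 20% |

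**Step 2: one case inside the first row.** Suppose that 8 of the 10 children at grade 2 or more fall below it, 2 stay, and 5 of the other 10 rise. Then w = 2 + 5 = 7, or 7/20 = 35%. New cases are 5/20 = 25% of all children and 5/10 = 50% of those who began below grade 2. The same two percentages would appear with no new cases at all (7 of the 10 stay, none rise). A shift table separates these cases.

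**Step 3: highest post-baseline score.** If 4 children are at grade 2 or more at Week 2 and 4 at Week 4, they may be the same children or different ones. The number ever affected lies between 4 and 4 + 4 = 8, or 20% to 40% of 20. This range remains even when every Baseline score is 0.

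**Step 4: a limit of counting increases.** Take a child scored 2 at Baseline because of plaque redness. After Baseline the rater follows the instruction and grades irritation alone, giving 1 or 2. The change is −1 or 0, so genuine new irritation is not counted as an increase, although it does appear in the by-visit row.

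**The case against.** The strongest reply is that the by-visit table hides no one. A child newly at grade 2 or more is counted in that visit's row, so w is an upper limit on new cases. In Step 2 the row shows 35% when 25% are new, which overstates irritation. This stands. A reader might infer that clearing psoriasis masks new irritation in the planned table. The documents do not support that: the misreading arises only when a later row is subtracted from the Baseline row, and the SAP plans no such subtraction.

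Second, raters who follow the instruction give post-Baseline scores that reflect irritation at face value, and grade 0 of a scale of irritation reactions fits an untreated plaque. This also stands, and if every Baseline score is 0 nothing is lost within a visit. But the instruction does not reach the Baseline score, so the plan depends on a condition that it does not state.

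Third, the listings let anyone trace about 20 children by hand. That is correct, so it would be wrong to say that the scores are reported only as percentages. A hand trace is still not a planned result, and SAP section 5 labels analyses added after database lock as post hoc.

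Fourth, more serious reactions have other routes: the adverse-event criterion, and the interruption rule in Protocol 7.9, which starts at a score of 5. This narrows the point to milder irritation.

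**Conclusion.** The point holds as a gap in the summary of one component of a primary endpoint. The plan defines a Baseline for the investigator score and makes no within-child use of it, and it summarizes no highest post-baseline score. By-visit percentages bound the number of children who worsened without identifying it, and a fall from Baseline is not evidence that no new irritation occurred.

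Under the assumed 50% then 35%, the bound is 0 to 7 of 20 children. Those rates are illustrative. The documents give no basis for the share of children with non-zero Baseline scores, so the real size is unknown and, within a visit, is nil if all Baseline scores are 0.

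It might also seem to follow that any increase over Baseline should become the headline tolerability result. Step 4 shows why not: if plaques are scored at Baseline but excluded afterwards, that count misses new irritation of equal or lower grade. It belongs beside the by-visit counts and should not replace them. The study is descriptive and no decision rule in the statistical analysis rests on this table, so neither the sample size nor any inference is affected.

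**What to change.** Keep the by-visit table and add the following to SAP 10.3:

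- a supplementary shift table of the Dermal Response score from the SAP 8.2 Baseline to Week 2, to Week 4 and to the highest post-baseline score;
- the number and percentage of children with any increase over their own Baseline, not as the sole or main result;
- the distribution of the highest post-baseline score.

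In Protocol 7.1.7 and schedule footnote e, state that the Dermal Response score grades irritation only. Existing plaque redness or elevation is then not scored at Baseline, in line with what raters are already told to do after Baseline.

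The cost is one more table from data already collected and a sentence of rater guidance, with no new visit, assessment or children. The remaining downside is the one in Step 4: for any child whose plaques were nevertheless scored at Baseline, the count of increases can miss new irritation of equal or lower grade. A footnote should therefore tell the reader to take it together with the by-visit counts.

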10.4. Vital Signs

Vital signs measurements and their change from baseline will be summarized at each study visit. A shift table will identify subjects who gain or lose $>5\%$ body weight over the course of the study.

10.5. Physical Examination

Physical examinations will be performed at Screening, Baseline, and Week 4. Clinically significant physical examination parameters will be captured as adverse events. Physical examination and abnormal values will be listed in a listing. No summary tables of physical examination are planned. Changes in physical examination will be described in the text of the final report.

10.6. Prior and Concomitant Medications

Prior and concomitant medication verbatim terms captured via the EDC system will be mapped to Anatomical/Therapeutic/Chemical (ATC) class and Preferred Names using the

World Health Organization (WHO) Drug Dictionary Enhanced version B3 March 2019 or later. Prior medications are any medication with onset prior to first dose of treatment, even if the medication is continued after first dose. Concomitant medications are any medication with first dose on or after the day of first dose of treatment.

Prior and concomitant medications will be summarized by WHO ATC class and preferred name. These summaries will present the number and percent of subjects using each medication. Subjects may have more than one medication per preferred name. A subject is counted once if one or more medications is reported for the subject. Each summary will be ordered by descending order of incidence of ATC class and preferred term.

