**Table 1. Excluded Medications and Treatments**

Excluded Medications and Treatments	Washout Period Prior to Baseline
Systemic treatment with biological therapies with a possible effect on psoriasis vulgaris within the following time periods prior to Baseline/Day 1	
Etanercept	4 weeks
Adalimumab, infliximab	8 weeks
All other Biologics	12 weeks or 5 half-lives, whichever is longer
All other therapies with a possible effect on psoriasis vulgaris	
Oral/systemic corticosteroids, retinoids, apremilast, methotrexate, cyclosporine and other systemic immunosuppressants	4 weeks
PUVA or NBUVB phototherapy	4 weeks
Sedating antihistamines	1 week
Topical anti-psoriasis medications (e.g., topical corticosteroids, vitamin D analogs, prescription shampoos) (except for emollients)	1 week
Strong cytochrome P-450 CYP3A4 inhibitors e.g., indinavir, neflifinavir, ritonavir, clarithromycin, itraconazole, ketoconazole, nefazodone, saquinavir, suboxone and telithromycin	2 weeks
Strong cytochrome P-450 CYP3A4 inducers e.g., efavirenz, nevirapine, glucocorticoids, barbiturates (including phenobarbital), phenytoin, rifampin, and carbamazepine	2 weeks
Tanning beds, other light emitting devices	4 weeks
Investigational drugs	30 days or 5 half-lives, whichever is longer

**Note:** Eye and ear drop and nasal corticosteroid preparations are allowed. Inhaled corticosteroid preparations are allowed if used for a stable condition and at a stable dose for > 28 days before screening and are continued at the same dose throughout the study.

Non-medicated emollients, moisturizers and sunscreens will be allowed as used normally by the subjects. These can be applied only to non-treated areas as needed and should not be used within 12 hours of a study visit.

A tar-containing or dandruff shampoo (zinc pyrithione or selenium sulfide) is allowed for treatment of the scalp. Concomitant other medications for chronic conditions (eg, NSAIDs, statins, anti-hypertensives) are permitted unless specifically prohibited in the Protocol.

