Generally, the addition of new medications, including nonprescription medications, during the course of the study is discouraged. However, the short-term use of a medication may be authorized by the Investigator. The Investigator must make the decision to authorize the use of any such a medication only after consideration of the clinical situation, the potential for masking symptoms of a more significant underlying event, and whether the use of the medication will compromise the outcome or validity of the clinical investigation. If medication is required, the name, strength, frequency, duration of use, and reason for use will be recorded in source documents and entered into the Case Report Forms. Medications which have been used chronically by subjects, in particular statins and anti-hypertensives, are allowed for use during the study, except as prohibited in 'Exclusions' (Table 1).

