  - c. Subjects are approved to continue applying IP post Week 4 as long as the following have been discussed with the subject:

- Site should confirm the subject has adequate IP to continue dosing and if not ask the subject to return to the site to pick up additional IP or refer to the current IP Handling Plan for instructions on shipment of IP from site to subject.
- Confirm the subject has no AEs that would warrant discontinuation of the IP.
- Site should discuss any new or ongoing conmed(s) and determine if the use of any warrant having the subject stop IP application or not.
- For any female subject of childbearing potential that site should discuss and confirm the subject has continued her methods of ensuring pregnancy does not occur. Any deviation from these methods should be discussed further and the site should determine if IP should be halted or contact the medical monitor or Arcutis if they have any questions. A pregnancy test can be performed at the next onsite visit (this is applicable to prior visits being missed due to COVID-19 as well).
- Subjects are approved to continue dosing for up to 14 days past Week 4 until they return the clinic for the Week 4 visit. After this, sites should reach out to the Medical Monitor and/or Arcutis directly for approval to have subjects continue dosing.
- All the above discussions must be documented in the source.

d. If available, home health nurse visits could be considered for collection of Vital Signs and Clinical Labs.

e. In the event a subject is quarantined, has symptoms, or is confirmed positive for COVID-19, it is the Sponsor's opinion that IP can continue, assuming no other contraindications.

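### SAP 10.6 classifies medications by start date alone, so a drug started before Day 1 and taken throughout treatment is never counted as concomitant

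*SAP*

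**What the plan says.** SAP 10.6 gives two definitions. The first is "Prior medications are any medication with onset prior to first dose of treatment, even if the medication is continued after first dose". The second is "Concomitant medications are any medication with first dose on or after the day of first dose of treatment". The section then plans summaries by ATC class and preferred name, with the count and percentage of subjects using each medication. No other sentence in the SAP counts a continuing drug as concomitant.

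The protocol has no formal definition of either term. Section 8.3.5 handles prior and concomitant medication together and sets no boundary between them. Its usage elsewhere is consistent:

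- The note to Table 1 (section 6.8) says "Concomitant other medications for chronic conditions (eg, NSAIDs, statins, anti-hypertensives) are permitted unless specifically prohibited in the Protocol".
- The same note says "Inhaled corticosteroid preparations are allowed if used for a stable condition and at a stable dose for > 28 days before screening", and adds the condition that they "are continued at the same dose throughout the study".
- Section 6.8 also says "Medications which have been used chronically by subjects, in particular statins and anti-hypertensives, are allowed for use during the study", apart from those excluded in Table 1.
- Exclusion criterion 2 (section 6.5.2) speaks of changes to concomitant medication, which presupposes a drug already in use.
- Appendix 6 tells sites to ask about concomitant medication that is either new or ongoing.
- The schedule in section 2 collects concomitant medications from the Screening visit onward.

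**The concern.** A concomitant medication table is normally read as showing what subjects were taking while exposed to study drug. Under SAP 10.6 it would show only what they started once treatment began. The protocol steers away from such starts: "Generally, the addition of new medications, including nonprescription medications, during the course of the study is discouraged". Long-term drugs that run alongside the cream all fall under prior. There they share a category with drugs that were stopped before Baseline to meet the Table 1 washout periods.

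This matters because the study is open-label with a single treatment and no control arm, and its primary endpoints are PK, safety and tolerability. Reading an adverse event or an unusual trough concentration requires knowing what else the child was taking at the time. The protocol itself treats co-medication as relevant to exposure, since it restricts strong CYP3A4 inhibitors and inducers before and during treatment. That does not show that any permitted drug alters the PK results. It does show that use during treatment is something the report should display correctly.

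**Working it through.** The plan states no figure to reproduce. The check applies the two SAP definitions to each possible start and stop pattern.

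| Pattern | Taken during treatment? | Prior under SAP 10.6 | Concomitant under SAP 10.6 |
|---|---|---|---|
| Started and stopped before Day 1 | No | Yes | No |
| Started before Day 1, continued | Yes | Yes | **No** |
| Started on Day 1, before the first application | Yes, if continued | Yes | Yes |
| Started after Day 1 | Yes | No | Yes |

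The second row is the problem. The prior definition expressly keeps continued drugs, and the concomitant definition tests only the date of the drug's first dose. No reading of the two sentences places a continued drug under concomitant. The two categories overlap only for a drug started on Day 1 before the application.

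**Permitted inhaled corticosteroids**

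- Inputs: stable dose for more than 28 days before screening and continued throughout (Table 1 note); screening 0 to 21 days before Day 1 (up to 3 weeks, section 2); 28 days of treatment.
- Screening on Day 1: start is more than 28 + 0 = 28 days before first dose.
- Screening 21 days earlier: start is more than 28 + 21 = 49 days before first dose.
- Classification in both cases: prior yes, concomitant no.
- Use during treatment if the protocol condition is met: 28 of 28 days.

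The concomitant count for this class is therefore 0 by construction.

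**Possible size in the table**

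The documents do not say how many children take chronic medication, so the number k of continued users of a given drug is an assumption. The denominator is the planned sample of about 20.

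| Assumed k | True use during treatment, k/20 | Contribution to concomitant count |
|---|---|---|
| 1 | 1/20 = 5% | 0 |
| 2 | 2/20 = 10% | 0 |
| 4 | 4/20 = 20% | 0 |

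The zeros follow from the rule and need no assumption. Only the middle column depends on k.

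**The case against.** The strongest reply is that this is a disclosed convention and not an error. SAP 10.6 says plainly that continued drugs stay under prior, so an attentive reader can interpret the tables. The protocol passages that use the term differently are instructions to sites about what is permitted and what to ask; they do not set table categories, so no formal protocol definition is contradicted. This stands as far as it goes. However, an explicit rule can still produce a table that does not show what its title says, and the SAP's usage departs from every use of the term in the protocol passages listed above.

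The second reply is that the harm depends on table layout. The list of tables is in a separate document (SAP section 12), and SAP 10.6 suggests separate summaries without settling the matter. In one combined table each continued drug would appear. That is correct, and the understatement of concomitant use is conditional on separate tables. A combined table would still mix stopped and continued drugs, so under neither layout would a planned table isolate use during treatment.

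The third reply is that nothing is lost. Protocol 8.3.5 requires a by-subject listing, SAP section 5 lists individual subject data, and a prohibited drug that was not stopped should also appear as a protocol deviation (SAP 7.2). With about 20 children a reviewer can go to the listing. This is accepted and limits the consequence to the summary tables.

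It is also true that the frequency of chronic medication is unknown, and that the CRF is not available for review, so nothing can be inferred about a gap in it.

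**Conclusion.** The concern holds. As written, SAP 10.6 gives the wrong count and percentage for co-medication during treatment, because a drug continued from before Day 1 cannot enter the concomitant category. For permitted inhaled corticosteroids the count is 0 regardless of true use. For any other continued drug the shortfall equals the number of children taking it: 5% to 20% of the sample if 1 to 4 of about 20 do so, a range that is assumed.

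The effect on the concomitant summary assumes that prior and concomitant drugs are tabulated separately. The consequence is descriptive only; no endpoint, analysis population or test depends on it. It should be corrected because every analysis in this study is descriptive, so the tables depend on accurate labels, and because the correction costs almost nothing.

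**What to change.** Replace the two definitions in SAP 10.6 along these lines:

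- Concomitant: any medication taken on or after the first application of study drug, whatever its start date. This includes drugs that are ongoing and drugs stopped on or after that date.
- Prior: any medication stopped before the first application. Alternatively, keep the present prior definition and let a continued drug count in both categories, with a table footnote saying so.

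Confirm that the CRF records a stop date or an ongoing flag for every medication. The documents do not say whether it does; for drugs authorised during the study, protocol 6.8 lists name, strength, frequency, duration of use and reason.

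The cost is two SAP sentences, that check and the matching programming rule. No new data collection is needed if the CRF field exists. The change should be made before database lock, since SAP section 5 labels analyses added after lock as post hoc.
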